7.3. Unscheduled Visits

If, during the investigation, a subject requires an unscheduled visit to the clinical site, the following information will be collected at a minimum:

- Chief complaint prompting the visit. If the reason is an adverse event, the applicable eCRF for the adverse event must be completed and subject record completed as appropriate
- Date and time of the visit and all procedures completed at the unscheduled visit
- Review of adverse event and concomitant medications
- Documentation of any test article dispensed or collected from the subject, if applicable
- Slit lamp findings (using the Slit Lamp Classification Scale)

If the Investigator withdraws a subject from the study, the final study visit case report forms must be completed indicating the reason(s) why the subject was withdrawn. The subject record must be completed documenting the date and primary reason for withdrawal and the study CRA notified.

Any ocular and non-ocular Adverse Events that are ongoing at the time of the study visit will be followed by the Investigator, within licensure, until they have resolved, returned to pre-treatment status, stabilized, or been satisfactorily explained. If further treatment i.e., beyond licensure is required, the subject will be referred to the appropriate health care provider.

The following information will be collected during an unscheduled visit.

Unscheduled Visit		
Step	Procedure	Details
U.1	Chief Complaints	Record the subject's chief complaints for reasons for the unscheduled visit

Unscheduled Visit			
U.2	Adverse Events and Concomitant Medications Review	Review the subject's concomitant medications and record any changes from the previous study visit.	
U.3	Subject Reported Ocular Symptoms	Subjects will respond to a verbal open-ended symptoms questionnaire.	████████
U.4	Entrance VA	Record the entrance distance and near visual acuity (OD, OS and OU) to the nearest letter. For near measures use the ETDRS 2000 Series Chart 1 or 2. The acuity will be recorded to the nearest letter OD, OS and OU.	████████
U.5	Subjective Sphero-cylindrical Refraction	An optimal, binocular balanced distance sphero-cylindrical refraction will be performed. Record the refraction and distance visual acuity to the nearest letter.	████ ████████
U.6	Biomicroscopy	FDA Slit Lamp Classification Scale will be used to grade the findings and determine eligibility. For the conjunctival redness █████ 0.5 unit increments will be used in the grading. Corneal Staining Assessment █████ will be graded in 1.0 increments. If the clearance of the fluorescein needs to be expedited, preservative-free rewetting drops or saline may be instilled.	████ ████████ ████████
U.7	Lens Dispensing	Additional study lenses may be dispensed when required.	
U.8	Lens Fit Assessment:	Evaluate and grade lens centration, primary gaze movement, upgaze movement and tightness (push-up test). The subject should not proceed to wear the lenses if any of the following is observed: 
• presence of limbal exposure (appearance of clear cornea) in any gaze• presence of edge lift• presence of unacceptable movement (excessive or insufficient) in all three movement categories (primary gaze,	████

Unscheduled Visit			
		
upgaze, and push-up).
 
If either lens is deemed unacceptable, the subject will be discontinued from the study. Remove the lenses, perform a slit-lamp evaluation, and complete the Final Evaluation form.
	
U.9	Exit Visual Acuity	
Record the subject's exit distance and near visual acuity (OD, OS and OU) to the nearest letter.
 
For near measures use the ETDRS 2000 Series Chart 1 or 2. The acuity will be recorded to the nearest letter OD, OS and OU.
	[REDACTED]

7.4. Laboratory Procedures

Not Applicable

8. SUBJECTS COMPLETION/WITHDRAWAL

8.1. Completion Criteria

Subjects are considered to have completed the study if they:

- provided informed consent
- they are eligible
- completed all study visits

8.2. Withdrawal/Discontinuation from the Study

A subject will be withdrawn from the study for any of the following reasons:

- Subject death during the study period
- Subject withdrawal of consent
- Subject not compliant to protocol
- Subject lost to follow-up
- Subject no longer meets eligibility criteria (e.g. the subject becomes pregnant)
- Subject develops significant or serious adverse events causing discontinuation of study lens wear
- Subjects who have experienced a Corneal Infiltrative Event (CIE)
- Investigator's clinical judgment regarding the subject safety reasons (that it is in the best interest of the subject to stop treatment)
- Subject missed two consecutive study visits
- Subject not compliant with study lens wear schedule

- Subject not successfully dispensed due to lack of efficacy and safety including poor vision, poor comfort or unacceptable fit

For discontinued subjects, the Investigator will:

- Complete the current visit (scheduled or unscheduled)
- Complete the Final Evaluation, indicating the reason that the subject was discontinued from the study
- Record the spherocylindrical refraction with best corrected distance visual acuity
- Collect used test article(s) (worn or brought to the visit) from the subject and discard them, unless otherwise stated in Section 6.7
- Collect all unused test article(s) from the subject

An additional subject may be enrolled if a subject discontinues from the study prematurely.

In cases where a subject is lost to follow-up, every possible effort must be made to contact the subject and determine the reason for discontinuation/withdrawal. The measures taken to follow up must be documented including two written attempts and a certified letter (or equivalent) as the final attempt.

9. PRE-STUDY AND CONCOMITANT INTERVENTION/MEDICATION

Concomitant medications will be documented during screening and updated during the study. Disallowed medications and therapies are medications or therapies that contraindicate contact lens wear. See the Exclusion criteria for specific details.

10. DEVIATIONS FROM THE PROTOCOL

Investigator will notify study sponsor upon identification of a protocol deviation. Major protocol deviations must be reported to the sponsor within 24 hours after discovery of the protocol deviation. The Investigator will report deviations per IRB/IEC requirements. All deviations will be tracked, and corrective actions implemented as appropriate.

If it becomes necessary for the Investigator to implement a deviation in order to eliminate an immediate hazard to the trial subject, the Investigator may implement the deviation immediately without notification to the sponsor. Within 24 hours after the implemented deviation, the Investigator must notify and provide the rationale to the Sponsor and, as required, the IEC/IRB.

11. STUDY TERMINATION

If more than 2 subjects in the investigational soft contact lens group develop serious expected (e.g., definite or probable MK) or unexpected device related adverse events, the study will be suspended. Upon review and consultation with IRB, DMC, and JJVC safety review committee, the study may be terminated. This potential stopping rule is established based on our trial involving approximately 200 subjects wearing the investigational soft contact lens for up to 3 years with an assumed MK rate that is below 0.2% per patient-year. The rate of 0.2% per

patient year is the established rate for extended wear lenses in adults, which was requested by the FDA as a criterion for evaluating a contact lens for pediatric use in an FDA response to a pre-IDE submission. To be conservative, 200 independent patient years were used in the calculation. The probability of observing 2 cases or more incidents of MK is 0.061, and 3 cases or more incidents of MK is 0.007 (given an MK rate of 0.2% per patient year).

The occurrence of one or more Unanticipated Serious Adverse Device Effect (USADE), or any SAE where the relationship to study agent cannot be ruled out, may result in stopping further dispensing of test article. In the event of a USADE or SAE, the Sponsor may unmask the treatment regimen for the subject(s) and will discuss this with the Investigator before any further subjects are enrolled.

The Sponsor will determine when a study will be stopped. The Principal Investigator always has the discretion to initiate stopping the study based on patient safety or if information indicates the study's results are compromised.

JJV reserves the right to terminate the study at any time for any reason. Additionally, the IEC/IRB reserves the right to terminate the study if an unreasonable risk is determined. The study can be terminated by the Principal Investigator at the individual clinical site due to specific clinical observations, if in their opinion, after a discussion with JJV, it is determined that it would be unwise to continue at the clinical site.

JJV (and the IEC/IRB and DMC, if applicable) will evaluate all adverse events. If it is determined that an adverse event presents an unreasonable risk, the investigation, or that part of the investigation presenting the risk, will be terminated, as soon as possible.

Should the study be terminated (either prematurely or as scheduled), the Investigator will notify the IEC/IRB and Regulatory Authority as required by local regulatory requirements.

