1.4. Summary of Known Risks and Benefits to Human Subjects

The Investigational multifocal contact lenses are designed as a continuous asphere providing for the correction of refractive spherical ammetropia and presbyopia. The material is a silicone hydrogel material, senofilcon A.

The intent of the Study lenses are daily wear, reusable lens that the subject wears while awake. These lenses are not intended for extended wear. Anticipated risks and adverse reactions with this lens are similar to other soft daily wear contact lenses used to correct presbyopia. A listing of examples of adverse reactions is found in the Section 13 of this protocol. The investigator should follow normal clinical guidelines regarding examination and care of subjects who participate in this trial. For the most comprehensive clinical information regarding the JJV Investigational senofilcon-A multifocal lens refer to the Investigator Brochure.

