4. STUDY DESIGN AND RATIONALE

4.1. Description of Study Design

The clinical study is a randomized-controlled, double-masked, crossover clinical trial. There are two study treatments. A total of approximately 50 eligible hyperopic subjects will be targeted to complete the study. The first Test article will be dispensed for 3 ± 1 days and an optimization visit will occur. The final lens pair will be dispensed for 12 ± 2 days and the at

the follow-up the final lens measurements will occur. Subjects will complete a 7 ± 3 days washout between each fitting. The second study lens will then be fit based on the power of the lenses dispensed at the optimization visit of the first lens and the above sequence repeated. The second lens will not be optimized.

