4.3. Enrollment Target and Study Duration

A total of approximately 60 eligible subjects will be enrolled with 50 targeted to complete the study. The study will last approximately 2-4 months.

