4.13	Subjective Lens Fit Assessment	
Evaluate overall lens fit acceptance (acceptable or unacceptable) based on centration, movement and other fitting characteristics.
 
An unacceptable fit is deemed by one of the following criteria:
 
 • limbal exposure at primary gaze or with extreme eye movement; • edge lift; • excessive movement in primary and up gaze; or • insufficient movement in all three of the following conditions: primary gaze, 	[REDACTED]

		
up gaze, and Josephson push up.
 
If either lens is deemed unacceptable, the subject will be discontinued from the study. Remove the lenses, perform a slit-lamp evaluation, and complete the Final Evaluation form.
	
4.14	PRO Post-Fit Questionnaire	
The subject will evaluate the vision characteristics, comfort characteristics, handling characteristics, and visual symptoms of the study lenses using the PRO questionnaire.
	
4.15	Distance and Near Exit Visual Acuity	
Distance and near Snellen visual acuity will be measured for each eye with the study contact lenses in place.
 
For near measures use the ETDRS 2000 Series Chart 1 or 2. The acuity will be recorded to the nearest letter OD, OS and OU.
 
Note: The distance visual acuity must be at least 20/30 OU for the lenses to be dispensed.
	████████
4.16	Dispensing Criteria	
The lenses will be dispensed for 12 ± 2 days.
 
 • Distance Snellen acuity equal to or better than 20/30 OU • Subject must indicate that the vision is acceptable. • Subject must indicate that the comfort of the lenses is acceptable. • Lenses must have an acceptable general lens fit. 	
4.17	Patient Instructions	
Instruct the Subject the following:
 
 • The lenses will be worn on a daily wear basis. • OPTI-FREE® Replenish® solution will be used in a rub regime to disinfect and store the lenses each night in the lens case provided. • If determined necessary by the Investigator sterile non-preserved rewetting drops may be dispensed to be used as needed for dryness. • Subjects will be instructed to wear lenses 	

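### Section 11 supports its suspension threshold with microbial keratitis probabilities for 200 patient-years, while this trial has about 3 to 5; and the Synopsis and Section 11 contradict each other on the single-event stopping rule

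*Combined protocol and SAP*

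**What the plan says.** **The multi-subject rule (Section 11, first paragraph).** The study will be suspended if more than 2 subjects in the investigational lens group have serious expected or unexpected device-related events. The stated basis is: "This potential stopping rule is established based on our trial involving approximately 200 subjects wearing the investigational soft contact lens for up to 3 years". The assumed MK rate is 0.2% per patient-year. Of that rate the text says "patient year is the established rate for extended wear lenses in adults", adding that the regulator asked for it as a criterion for pediatric use. The calculation uses 200 patient-years, and the result is: "The probability of observing 2 cases or more incidents of MK is 0.061, and 3 cases or more incidents of MK is 0.007".

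**This trial.** Section 4.3: "A total of approximately 60 eligible subjects will be enrolled with 50 targeted to complete the study". Section 3.2 limits age to 40 to 70 years. Section 1.4: "These lenses are not intended for extended wear". Section 4.1 gives wear of the first lens in two steps: "The first Test article will be dispensed for 3 ± 1 days and an optimization visit will occur", then "The final lens pair will be dispensed for 12 ± 2 days". For the second lens, Section 7.2, Visit 4, step 4.16 says: "The lenses will be dispensed for 12 ± 2 days". Both lenses are investigational (Section 6.1, Table 1), and each subject is assigned to wear both.

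**The single-event rule.** The Synopsis (Study Termination row) and the second paragraph of Section 11 both cover a single unanticipated device effect, or a single serious adverse event (SAE) whose link to the study product cannot be excluded. They use different verbs, terms and actors, set out side by side under the working.

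**The concern.** A probability printed beside a stopping threshold tells an ethics committee or safety reviewer how often the threshold would be crossed by chance at an acceptable event rate. That holds only if the exposure behind it is the exposure of the trial in hand. Here the description differs from this protocol in number of subjects, duration, wear modality and the population for which the rate was requested. It also refers to an investigational lens group, which a crossover of two investigational lenses does not have. A reader would take 'more than 2' to have been calibrated to this study, and nothing in the document shows that it was.

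The conflict in the single-event rule bears more directly on conduct. With so little exposure, a first possibly related SAE would be acted on well before a third case, so the single-event rule is the safeguard most likely to operate. After such an event a site needs one answer on whether dispensing stops, and one on whether a discussion must take place before further enrolment.

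**Working it through.** **1. Reproduce the printed figures.** Inputs from Section 11: 200 patient-years and a rate of 0.002 per patient-year.

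- Binomial with n = 200 and p = 0.002: P(≥2) = 0.0614 and P(≥3) = 0.0078.
- Poisson with mean 0.4: 0.0616 and 0.0079.
- With 600 patient-years (200 subjects × 3 years): 0.337 and 0.120, which do not match.

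The printed 0.061 is therefore right for 200 patient-years. The printed 0.007 is 0.0078 truncated; it rounds to 0.008. The arithmetic is sound for its own inputs.

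**2. Exposure in this trial.** Patient-years = subjects × days of wear ÷ 365.25. Inputs are 50 to 60 subjects (Section 4.3) and the visit schedule of 3 ± 1, 12 ± 2 and 12 ± 2 days (Sections 4.1, 7.1 and 7.2).

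- Nominal wear: 3 + 12 + 12 = 27 days. Minimum: 2 + 10 + 10 = 22. Maximum: 4 + 14 + 14 = 32.
- Nominal: 50 × 27 ÷ 365.25 = 3.70; 60 × 27 ÷ 365.25 = 4.44 patient-years.
- Extremes: 50 × 22 ÷ 365.25 = 3.01; 60 × 32 ÷ 365.25 = 5.26 patient-years.
- Ratio to 200: 200 ÷ 5.26 = 38, and 200 ÷ 3.01 = 66.

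**3. Like-for-like probabilities at the protocol's own rate.** With μ = 0.002 × patient-years, P(≥2) = 1 − e^(−μ)(1 + μ) and P(≥3) = 1 − e^(−μ)(1 + μ + μ²/2).

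| | Printed | 3.01 patient-years (μ = 0.0060) | 5.26 patient-years (μ = 0.0105) |
|---|---|---|---|
| P(≥2 MK) | 0.061 | 1.8 × 10⁻⁵ | 5.5 × 10⁻⁵ |
| P(≥3 MK) | 0.007 | 3.6 × 10⁻⁸ | 1.9 × 10⁻⁷ |

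These cover MK only. The rule also counts other device-related events, for which no rate is given, so the overall chance of reaching the threshold cannot be computed.

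**4. Sensitivity to the wear time.** Sections 2.3 and 4.2 speak of 14 to 20 days of wear per lens. Taking 20 days for each gives 60 × 40 ÷ 365.25 = 6.57 patient-years, still 30 times less than 200, with P(≥2) = 8.6 × 10⁻⁵ and P(≥3) = 3.7 × 10⁻⁷. The visit schedule does not allow 40 days, because the second lens is dispensed for at most 14. Section 4.1 says the sequence is repeated for the second lens, which would give up to 36 days and 60 × 36 ÷ 365.25 = 5.91 patient-years. It also says that lens is not optimized, and the schedule has no such visit.

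**5. The single-event rule side by side.**

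| Element | Synopsis | Section 11 |
|---|---|---|
| Trigger term | UADE | USADE |
| Trigger, second limb | SAE with link not excluded | the same |
| Effect on dispensing | *will* stop | *may* stop |
| Actor | Sponsor Medical Monitor | Sponsor |
| Discussion with investigator before further enrolment | *may* | *will* |

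The two verb conflicts run in opposite directions, so neither text is uniformly the stricter. Section 13.1 defines UADE only. Section 13.4.1 puts 'Serious' in parentheses inside the UADE heading, which suggests that the two terms mean the same thing, but no section says so.

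**The case against.** The strongest reply is that 'more than 2' is a clinical backstop that needs no calibration, and that the practical consequence is small. Serious events reach the sponsor within 24 hours (Sections 13.4 and 13.4.1). Subjects whose serious event stops lens wear are withdrawn (Section 8.2). The sponsor, the IRB and the investigator each hold separate stopping powers (Section 11). All of this stands, and it limits the point to minor. It does not make the printed probabilities applicable.

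On the single-event rule, one could say that a synopsis only summarises, and that Section 11 leaves it to the sponsor to decide when the study stops. But a summary should not turn *may* into *will*, and nothing ranks it below the body. The sponsor's authority also concerns stopping the study, not dispensing. It is fair that aligning both places on *may* would remove the contradiction as well; choosing *will* is a judgement in favour of caution.

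A reader might infer more than the documents support:

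- That the justification was taken from another identifiable trial. Section 11 calls it the sponsor's own trial and names no other study. The documents show only that the description does not fit this one.
- That the threshold is wrong or can never be reached. The tail probabilities are for MK alone at an extended-wear rate, and the rule counts other events too.
- That subjects are unprotected. The other safeguards remain.
- That exposure could be 6.6 patient-years. That needs a wear time the visit schedule rules out.

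**Conclusion.** The point holds as a minor inconsistency in the safety text, in two parts.

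First, the MK probabilities given for the suspension rule describe 200 patient-years, while this trial has about 3.0 to 5.3 by its visit schedule, 38 to 66 times less. They therefore give no usable basis for 'more than 2' in this study. This rests on 50 to 60 subjects wearing both lenses for the scheduled time, with replacement subjects not counted; no reading of the wear time changes the conclusion. The 0.2% rate is used only to compare with the printed figures, not as an estimate for these lenses.

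Second, the single-event rule cannot be followed as written in both places. This follows from the texts alone and needs no assumption. It is the part that could change what a site does.

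No endpoint, sample size or efficacy analysis is touched.

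**What to change.** **Section 11, first paragraph.** Delete everything from the sentence that introduces the 200-subject trial through the sentence with the two probabilities. Do not substitute new probabilities at the extended-wear rate. Have the sponsor's safety team reconfirm or lower 'more than 2' for this trial's exposure, counting events on either study lens. State in one sentence that the threshold is a clinical-judgement backstop to the single-event rule.

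**Synopsis and Section 11, single-event rule.** Use identical wording in both places, with one term (UADE, as defined in Section 13.1) and one named actor. The safer choice is that dispensing *will* stop, and that the sponsor, through its Medical Monitor, *will* discuss the event with the investigator before further enrolment. If the sponsor wants dispensing to be able to resume after review, both places should say so explicitly; at present neither does.

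**Cost.** A text amendment in two places and one safety-team decision, with no added visits, procedures or subjects. The downside is a possible pause in dispensing after a single possibly related SAE.

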12. PROCEDURE FOR HANDLING PRODUCT QUALITY COMPLAINTS

A Product Quality Complaint (PQC) refers to any written, electronic, or oral communication that alleges deficiencies related to the identity, quality, durability, reliability, safety, effectiveness or performance of test articles after they have been released for clinical trial use.

Potential complaints may come from a variety of sources including but not limited to subjects, clinical research associates (CRA), clinical operations managers (COM), medical monitors, and site personnel, etc. The following are not considered product quality complaints:

- Subject satisfaction inquiries reported via "Subjective Questionnaires" and "Patient Reported Outcomes (PRO)"
- Clinical test articles that are stored improperly or damaged after receipt at the investigational site
- Lens replacements that occur due to drops/fall-outs

- Damage deemed by clinicians or clinical staff to be caused by handling by the user, and not indicative of a quality deficiency (i.e. tears, rips, etc.), only in situations where there is no deficiency alleged by the subject

Within 24 hours of site personnel becoming aware that a PQC has occurred, the PQC must be recorded in the EDC system, which will trigger an automatic email notification to the appropriate COM/CRA and Clinical QA representative. In cases where the EDC system in use is not configured to send automatic notifications or when an EDC system is not used, the COM/CRA is responsible for notifying Clinical QA upon discovery that a PQC has occurred.

Upon receipt of the EDC notification, the COM/CRA will contact the study site to collect additional information which will include:

- Date the complaint was received/recorded in the EDC System (Date of Sponsor Awareness)
- Who received the complaint
- Study number
- Clinical site information (contact name, site ID, telephone number)
- Lot number(s)
- Unique Subject Identifier(s)
- Indication of who first observed complaint (site personnel or subject)
- OD/OS indication, along with whether the lens was inserted
- Any related AE number if applicable
- Detailed complaint description (scheduled/unscheduled visit, wear time, symptoms, resolution of symptoms, etc.)
- Eye Care Provider objective (slit lamp) findings if applicable
- Confirmation of product availability for return (and tracking information, if available), or rationale if product is not available for return (Refer to Form Control [REDACTED] for test article return instructions)

Once a complaint is received, it will be assessed by the COM, CRA, or trained site personnel to determine if it is an Adverse Event/Serious Adverse Event (AE/SAE). If the complaint results in an AE/SAE, the COM/CRA, or trained site personnel will follow Section 13 of this protocol. If the AE/SAE was potentially the result of a product quality related deficiency, these procedures also applies and will be executed in parallel.

In some cases, a PQC form may be generated in EDC by the site in error. In this event, the PQC forms will be marked “Intentionally Left Blank” or “ILB”. Justification for ILB must be documented.

